IMP infusion ^m	X ⁿ	X ^{o,p}																	
AE review	Continuous monitoring																		
Concomitant medications review	Continuous monitoring																		

	BL ^a	Study week																EDV ^b	SFV ^c
		1	2	3	4	5-7	8	9-11	12	13-15	16	17-23	24	25-35	36	37-47	48		
Study day (±2)	1	8	15	22	29	36-50	57	64-78	85	92-120	127	134-162	169	176-246	253	260-330	337		393

BL = baseline; clinESSDAI = clinical; ESSDAI; D = day; d/c = discontinuation; ECG = electrocardiogram; EDV = early discontinuation visit; ESSDAI = EULAR Sjögren’s syndrome disease activity index; ESSPRI = EULAR Sjögren’s Syndrome Patient-Reported Index; EULAR = European Alliance of Associations for Rheumatology; ICF = informed consent form; IgG = immunoglobulin G; IMP = investigational medicinal product; IV = intravenous; MFI = Multidimensional Fatigue Inventory; NA = not applicable; OSS = ocular staining score; PASS = patient acceptable symptom state; PCR = polymerase chain reaction; PD = pharmacodynamics; PGA = patient global assessment; PK = pharmacokinetics; RF = rheumatoid factor; SCR = screening; SFV = safety follow-up visit; SF-36 = 36-Item Short Form Survey; SGUS = salivary gland ultrasonography; SS-A = Sjögren’s syndrome-related antigen A; SS-B = Sjögren’s syndrome-related antigen B; SWSF = stimulated whole salivary flow; UWSF = unstimulated whole salivary flow; W = week.

^a BL will coincide with the final visit of a previous qualifying study. Grayed-out assessments may be conducted as part of the previous qualifying pSS studies.

^b The EDV will be performed within 7 days after last dose administration.

^c Participants will attend a safety follow-up visit 56 ± 3 days after the final IMP administration.

^d Weight mandatory at baseline.

^e Vital signs will be measured before collecting any blood sample or administering IMP infusions.

^f On IMP administration visits, blood samples must be collected predose (preferably within 2 hours before the infusion). On other visits, a blood sample may be collected at any time during the visit.

^h On IMP administration visits, blood samples for PK analyses will be collected predose (preferably within 2 hours before IMP administration). On other visits, a blood sample may be collected at any time during the visit.

ⁱ A PK sample will also be collected within 30 minutes after the end of IMP infusion.

^j The biological domain will remain blinded until the parent study is unblinded.

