4.3. Justification for Dose

Doses of efgartigimod 10 mg/kg either QW or Q2W will be administered. For responders a Q2W regimen has been selected to evaluate whether a less frequent dosing regimen can maintain clinical efficacy, while the QW regimen for nonresponders targets efgartigimod's to achieve a near maximal total IgG reduction (PD effect), thereby maximizing the chance of a clinical response on the efficacy outcomes in nonresponders.

As the hypothesis for treating pSS with efgartigimod is to reduce the pathogenic autoreactive IgG, the selected doses and dose regimen target a nearly maximal PD effect (ie, reduction of pathogenic IgGs). The chronic nature of pSS reflects the need for chronic treatment to maintain pathogenic IgG autoantibody suppression and symptom reduction.

The cumulative data from a phase 1 study in healthy adult subjects; phase 2 studies in participants with gMG, ITP, and pemphigus; phase 3 studies in gMG; and PK/PD modeling results demonstrate that a 10 mg/kg efgartigimod dose administered QW through IV infusion achieved 60% to 70% total IgG reduction, including the reduction of pathogenic autoantibodies. Maximal IgG reduction was associated with clinical efficacy observed in gMG, ITP, and pemphigus studies. Furthermore, this dose has been safe and well-tolerated in all study populations and has demonstrated similar PK and PD profiles across indications. Accordingly, the 10 mg/kg IV dose regimen (QW or Q2W) was selected for this study.

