8.6. Pharmacodynamics

Baseline and postbaseline PD blood samples will be collected predose on IMP administration visits (preferably within 2 hours before IMP administration) as described in the SoA (Section 1.3). At visits where the IMP is not administered, blood samples may be collected at any time during that visit.

Total IgG concentrations will be quantified at a diagnostic laboratory. Results will not be reported to investigative sites or other study personnel to maintain the parent study blind.

Participants will also be tested for anti-Ro/SS-A and anti-La/SS-B autoantibodies at the time points specified in the SoA (Section 1.3), as a part of secondary PD measures. All results will be blinded.

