3. STUDY DESIGN

3.1. General Description

This is a long-term, single-arm, open-label, multicenter extension of pSS qualifying efgartigimod studies designed to evaluate the long-term safety of efgartigimod in adult patients with pSS. Participants will be enrolled from both active and placebo arms of qualifying efgartigimod studies and receive efgartigimod intravenous (IV) 10 mg/kg over 48 weeks in the extension study without knowledge of their treatment assigned in the qualifying study. To be eligible to enroll in this study, participants must have completed the treatment period of the qualifying study and must not have permanently discontinued the investigational medicinal product (IMP) in that study.

Participants will receive efgartigimod 10 mg/kg by IV infusion either every 2 weeks (Q2W) or once weekly (QW). The dosing regimen is based on whether the participant is a responder or non-responder on day 1. ClinESSDAI assessments to determine responder status using the baseline will be conducted on day 1 and weeks 16 and 24. Responders will receive IV infusions Q2W. Non-responders will receive an infusion QW until such time that they are considered to be responders. If a participant is not a responder at week 24, they will be evaluated by the principal investigator (PI) for therapeutic failure.

- Therapeutic failure - the participant will discontinue study treatment.
- Not a therapeutic failure - the participant will continue QW dosing regimen. ClinESSDAI will be conducted at weeks 32, 36, 40, and 44 until confirming responder status and switching to Q2W dosing regimen. The PI will continue to evaluate the participant for therapeutic failure.

If the participant and/or investigator consider there to be a reduction in therapeutic effect once the patient has switched to Q2W, the participant will return for an unscheduled visit during which a clinESSDAI, a blood sampling for pharmacokinetic (PK) and ADA will be collected.

If there has been an increase in clinESSDAI score of ≥ 3 points and/or a change in score that reclassifies their disease from mild severity to moderate severity the participant will switch to QW dosing regimen and will remain on this dose regimen for the remainder of the treatment period.

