7.2. Output Presentations

For continuous variables, full descriptive statistics will only be presented if there are at least 2 non-missing observations. Alternatively, only the number of non-missing data points and mean are shown.

Descriptive statistics for safety and efficacy will include the number of non-missing data points, the arithmetic mean, the standard deviation (SD), the median, minimum, Q1, Q3, maximum, and for efficacy the standard error (SE) and 90% CI may be provided in addition (refer to output templates for details).

Mean, Q1, Q3 and median will be presented with one more decimal place than the measured values. SE and SD will be presented with two more decimal places than the measured values. Minimum and maximum will be presented with the same number of decimal places as the measured values.

Descriptive statistics for PD parameters will include the number of non-missing data points, the arithmetic mean, the SD, the SE, the 90% CI, the median, minimum, Q1, Q3, and maximum. Descriptive statistics of total IgG levels will be presented in $\mu\text{g/mL}$.

Serum PK concentrations will be summarized using descriptive statistics for $n > 2$ by study day and nominal time point using N (sample size), n (available data), arithmetic mean, SD, geometric mean, mean coefficient of variation (CV), CV%, the geometric CV%, minimum, median and maximum.

Concentrations that are BLQ will be treated as zero for the computation of descriptive statistics. If at least one BLQ value is reported at a specific time point, the geometric mean and geometric CV% for that time point will not be calculated. In addition, if one or more than half of the values per time point are BLQ, the arithmetic mean will be reported as BLQ and SD, CV%, GM, [geometric SD], and geometric CV% will not be calculated and shall be reported as not determined (ND); minimum, median, and maximum shall be reported as BLQ if applicable. If $n \leq 2$, only N, n, minimum, and maximum will be reported.

Copyright © 2009, 2010, 2012, 2016, 2018, 2019, 2021, 2024 IQVIA. All rights reserved. The contents of this document are confidential and proprietary to IQVIA Holdings Inc. and its subsidiaries. Unauthorized use, disclosure or reproduction is strictly prohibited.

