For the reporting of descriptive statistics for PK data, the mean and SD will be presented to one digit more precision than the source data except values ≥ 1000 which will be presented without the decimals and rounded to the nearest integer. The minimum, median, and maximum will be presented to the same precision as the source data. Coefficient of variation will always be reported to 1 decimal place. Individual serum concentrations will be reported as received by the bioanalytical laboratory.

Descriptive statistics for immunogenicity titer values will include the number of observed values, arithmetic mean, SE, 90% CI, median, Q1, Q3, minimum, maximum, the geometric mean, and geometric CV%.

For event-type safety data, the number and percentage of participants with an event will be shown. The denominator will be all participants in the analysis set.

For frequency tabulations and cross-tabulations, the denominator will be the number of participants. For tables where results are shown by analysis visit, the denominator will be the number of participants and analysis visit.

Missing values will not be included in the denominator count when computing percentages. For cross-tabulation of post-baseline results versus baseline results, a “missing” category will be shown for baseline results, if applicable. Percentages will be presented with 1 decimal place.

Summaries will be provided both for the overall study population as well as grouped according to treatment received in the parent study AGRX-113-2106 (efgartigimod or placebo). [Appendix 1](#) shows conventions for presentation of data in outputs.

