14. PHARMACODYNAMIC ANALYSIS

PD analyses will be performed in the SAF. PD endpoints include total IgG, Anti-Ro/SS-A, and anti-La/SS-B. PD endpoints will be summarized using descriptive statistics at each analysis visit. Actual values, changes from baseline, and percent change from baseline will be presented. In addition to the planned time points at baseline, week 4, 8, 12, 16, 24, 36, 48, and SFV, the following time points will also be shown:

- Maximum drop from baseline
- Minimum postbaseline value

Additionally, a line chart showing percent change in total IgG, Anti-Ro/SS-A, and anti-La/SS-B, over time will be prepared. If appropriate, the graphic presentation of percent change over time may be presented for all PD endpoints combined. All PD data will be listed.

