18. PHARMACOKINETIC ANALYSIS

PK analyses will be performed in the PKAS.

At IMP administration visits, PK blood samples will be collected predose (within the 2 hours before IMP infusion) and post-dose (within 30 minutes after the end of IMP infusion) at baseline and week 16.

A listing of PK blood sample collection times, derived sampling time deviations, and concentrations will be provided. A subject listing of all concentration-time data will be presented by study day and scheduled time point.

Serum concentrations will be summarized using descriptive statistics for efgartigimod. The pharmacokineticist will determine a strategy for dealing with data affected by protocol deviations or events which may impact the quality of PK concentration data on a case-by-case basis with input from the study physician, as needed. Examples of protocol deviations or events include, but may not be limited to the following:

- When a predose sample is taken after IMP administration.
- Postdose samples are collected following the occurrence of incomplete or incorrect dosing for the most recent prior dose administration.
- Any event related to sample collection, handling and storage that affects the integrity of the samples and/or the bioanalytical results.
- When predose PK samples are taken outside the visit windows.
 - The study visit windows are ± 2 days

In the case of an important protocol deviation or event, the PK data collected may be excluded from the summaries

and a reason for the exclusion of the data point will be added in the appropriate listing.
The strategy for the population PK analysis and any related exposure-response modeling utilizing the efgartigimod concentration and IgG data collected from this study will be outlined separately in the PK analysis plan.

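### The visible SAP does not split predose PK and PD summaries by dosing regimen, so each visit's pooled mean depends on the share of participants on Q2W

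*SAP*

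**What the plan says.** Two regimens run side by side. SAP 3.1: "Responders will receive IV infusions Q2W. Non-responders will receive an infusion QW until such time that they are considered to be responders". Protocol 4.3 gives the reason for the second: "For responders a Q2W regimen has been selected to evaluate whether a less frequent dosing regimen can maintain clinical efficacy".

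The summary rules do not name the regimen:

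- SAP 7.2, all outputs: "Summaries will be provided both for the overall study population as well as grouped according to treatment received in the parent study" (efgartigimod or placebo).
- SAP 7.2, cells for PK concentrations: "by study day and nominal time point using N (sample size), n (available data", followed by further statistics.
- SAP 14, for total IgG, anti-Ro/SS-A and anti-La/SS-B: "PD endpoints will be summarized using descriptive statistics at each analysis visit". A line chart of percent change over time is also planned.
- SAP 18: "Serum concentrations will be summarized using descriptive statistics for efgartigimod".

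SAP 15 adds one further breakdown, by ADA class, for mean concentration and mean percent change in total IgG. Regimen groups do appear elsewhere. SAP 13.1.5 uses three for clinESSDAI and ESSDAI, and SAP 11 (Table D) defines four regimen patterns for exposure.

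On timing, Protocol 8.6 says: "Baseline and postbaseline PD blood samples will be collected predose on IMP administration visits". Protocol 8.5 and the Schedule of Activities set the same rule for PK, with an extra sample within 30 minutes after the infusion at baseline and week 16.

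**The concern.** One visit label covers samples with a twofold difference in time since dosing. If the two regimens give different troughs, the pooled mean is a weighted average whose weights are the regimen shares at that visit. It can then move from visit to visit with no change within either regimen, or stay flat while the regimens diverge.

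The parent-arm split does not remove this and may inherit it. The first regimen depends on day 1 responder status, and response in the parent study may depend on what was received there. Part of any difference between parent arms in trough or IgG could therefore be regimen mix.

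Drug concentration, total IgG and the two autoantibodies are secondary endpoints. The plan reports clinESSDAI and ESSDAI by regimen, but not the exposure and IgG levels that would help explain those scores.

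**Working it through.** The plan states no figure on this point, so there is nothing to reproduce. The check covers sampling times, regimen mix and illustrative size.

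**1. Time since last dose.** The postbaseline PK and PD visits in the treatment period are weeks 4, 8, 12, 16, 24, 36 and 48 (Schedule of Activities). All are even weeks, so a participant established on Q2W is due a dose at each visit before week 48. The predose sample is then about 14 days after the previous dose, against about 7 days on QW. Week 48 has no dose, but the final doses are at week 46 (Q2W) and week 47 (QW), so the gap is again 14 against 7 days.

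**2. When the mix can change.** Scheduled switch points are day 1, week 16 and week 24, then weeks 32 to 44 for remaining nonresponders. A predose sample at a switch visit still reflects the earlier regimen. From week 4 to week 16 the mix therefore changes only through an unscheduled return to QW or through dropout. From week 24 on it also changes through switches to Q2W and through therapeutic failures stopping treatment. The visits exposed to a shifting mix are mainly weeks 24, 36 and 48.

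**3. Whether both regimens exist from day 1.** The synopsis and schema judge response against the qualifying-study baseline, and Table D includes patterns that start on Q2W. On that reading the mix can differ by parent arm from the start. Protocol 4.1 instead describes the baseline as the final qualifying-study visit, which would leave no change to measure on day 1. Those passages must be reconciled. The arithmetic below needs only that both regimens are populated at a visit.

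**4. Trough ratio (assumed model).** Take a linear one-compartment model at steady state with equal doses. With half-life t in days and x = 2^(-7/t), the QW trough is proportional to x/(1 - x) and the Q2W trough to x²/(1 - x²). Their ratio is R = x/(1 + x). Decay from day 7 to day 14 alone would give x; the factor 1/(1 + x) is the lower accumulation on Q2W. With share q on Q2W, pooled mean / QW mean = (1 - q) + qR.

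| Assumed t (days) | x | R | Pooled / QW at q = 0.5 |
|---|---|---|---|
| 3 | 0.198 | 0.166 | 0.583 |
| 4 | 0.297 | 0.229 | 0.615 |
| 5 | 0.379 | 0.275 | 0.637 |

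R stays below 0.5 for any half-life in this model.

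**5. Effect of a changing or unequal mix (t = 5, R = 0.275).**

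- If q rises from 0.3 to 0.7 across visits, the pooled trough falls from 0.782 to 0.492 of the QW mean with nothing changing within either regimen.
- If q is 0.6 in one parent arm and 0.3 in the other, the arm means are 0.4 + 0.6 × 0.275 = 0.565 and 0.7 + 0.3 × 0.275 = 0.783 of the QW mean.

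**6. IgG.** Protocol 4.3 gives a 60% to 70% reduction for QW and no Q2W figure. Take 65% for QW and let q rise from 0.3 to 0.7.

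- Q2W assumed 45%: pooled reduction goes from 0.7 × 65 + 0.3 × 45 = 59% to 0.3 × 65 + 0.7 × 45 = 51%.
- Q2W assumed 55%: pooled reduction goes from 62% to 58%.

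These are reductions from an untreated level. Participants from the parent efgartigimod arm enter with an OLE baseline taken after prior dosing, so their change from OLE baseline will look different.

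**7. BLQ rule.** Under SAP 7.2 a single BLQ value cancels the geometric mean for the whole time point. One BLQ trough at 14 days would therefore remove that statistic for QW participants too.

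**The case against.** The strongest case on the other side has five parts.

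- **The absence is not fully established.** SAP 7.2 points to Appendix 1, whose contents include presentation of treatment groups. Neither that appendix nor the output templates are in the public text, and SAP 13.2, 13.3 and 16 are redacted. This stands: a regimen layout there cannot be ruled out. The point is confined to SAP 7.2, 14 and 18, which are visible.
- **Other routes exist.** SAP 18 leaves population PK and exposure-response work to a separate plan, and such models can use actual dose times. Concentrations, PD data and administrations are also listed. This stands in part: the information can be recovered. However, Protocol 9.3.1 makes the population analysis optional, and listings do not summarise an endpoint.
- **The stated Q2W question is clinical efficacy.** SAP 13.1.5 already splits clinESSDAI and ESSDAI by regimen, and no regimen comparison is promised for PK or PD. This is correct. It makes the PK and PD split supporting information, not a missing planned analysis.
- **Not every sample is affected.** Baseline and 30-minute post-infusion samples are little affected, and the mix is nearly fixed up to week 16. This also stands. A reader might infer that no trend over visits can be interpreted; the switch schedule does not support that.
- **The yield is limited.** With about 30 participants, cells will be small, and SAP 7.2 reports only N, n, minimum and maximum when n is 2 or less. Regimen is assigned by response, so QW and Q2W groups differ for reasons other than dosing. Both limits stand and belong in the fix.

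**Conclusion.** The point holds as a modest, inexpensive improvement to descriptive summaries of secondary endpoints. In the visible governing sections, postbaseline predose PK and PD values are pooled across two dosing intervals, and the pooled mean depends on the share on Q2W.

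The size cannot be fixed from the documents. For troughs, the 0.58 to 0.64 figure rests on an assumed half-life of 3 to 5 days, a linear one-compartment model at steady state and an even split between regimens. For IgG, the distortion is small if Q2W suppresses nearly as well as QW.

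Two stronger readings are tempting and not supported. One is that parent arm is the only breakdown: SAP 15 also tabulates concentration and IgG change by ADA class, although that does not separate the regimens. The other is that the pooled means are bound to describe neither regimen: that requires both regimens to be populated at the visit and to differ materially, which the documents do not establish, least of all for IgG.

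**What to change.** In SAP 14 and 18, add descriptive tables and plots of predose concentration, total IgG, anti-Ro/SS-A and anti-La/SS-B at each visit, alongside the overall and parent-arm summaries:

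- Group by the regimen in force before the sample. A predose sample at a week 16 or week 24 switch visit counts under the earlier regimen. The whole-study patterns in Table D and SAP 13.1.5 are not suitable for this, because one participant can contribute samples under both regimens.
- Report actual time since last dose, from the recorded infusion dates and times.
- Show n in every cell and add individual profiles.
- Apply the BLQ rule within regimen.
- State that regimen is assigned by response, so QW against Q2W is descriptive and not a causal comparison.

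If Appendix 1 or the output templates already contain such a split, a cross-reference from SAP 14 and 18 is enough.

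The cost is some programming and extra columns, with no new data and no change to conduct. The main downside is sparse cells with about 30 participants, so regimen should not be crossed with parent arm by default.

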7.3. Multiple Comparisons/ Multiplicity

No multiple comparison adjustment or alpha sharing to be considered.

8. DISPOSITION AND WITHDRAWALS

All subjects who provide informed consent will be accounted for in this study.

8.1. Disposition

The number of participants will be summarized for FAS. The number of participants per country and site will also be provided using the FAS. The number of participants who completed or discontinued the treatment and/or the study along with the reason for discontinuation will be summarized using the FAS.

Participant disposition and withdrawals will be presented for the FAS.

The enrollment failures will be summarized using number of participants who signed the informed consent form.

Copyright © 2009, 2010, 2012, 2016, 2018, 2019, 2021, 2024 IQVIA. All rights reserved. The contents of this document are confidential and proprietary to IQVIA Holdings Inc. and its subsidiaries. Unauthorized use, disclosure or reproduction is strictly prohibited.

Data will be tabulated at least for:

- Number of participants in each analysis sets.
- number and percentage of participants enrolled, completed, or discontinued the study.
- number and percentage of participants for each study discontinuation reason.
- number and percentage of participants discontinuing treatment but continuing study assessments.

A listing of participant disposition will be prepared to present information about treatment discontinuation and study discontinuation.

